1.2 Sources of Materials

Research material obtained from the participants include responses to phone and online surveys, collected directly by our research team and entered directly within secure databases. Participants will also complete daily diaries, entered directly in to secure REDCap survey database. Research data will be obtained specifically for research purposes. Every effort will be made to maintain subject confidentiality, in accordance with HIPAA.

1.3 Potential Risks

The research protocol calls for non-treatment seeking smokers to be supplied with 4-week sample of varenicline, or not. Varenicline is an FDA-approved medication for smoking cessation, and all black-box warnings have been removed. Use of varenicline is entirely self-chosen, since this is one outcome, rather than prescribed. Varenicline is inarguably the strongest single-agent medication to facilitate smoking cessation. Questionnaires and interviews are all non-invasive and involve minimal risk to study participants. Potential risks are as follows:

1.3.1 Risk of using varenicline: Up through 2015, FDA required a black-box warning for varenicline, largely due to media/anecdotal reports of self-injury, including suicide. A number of reviews and meta-analyses of varenicline have shown safety.^{52,61-64,114} For example, in a pooled analyses of 10 varenicline RCTs, across 5,000 smokers, only insomnia was related to active medication.¹¹⁵

[figure not shown]
Table HS1: Review of Psychiatric Adverse Events: Pooled analyses of 10 Varenicline RCTs

	Varenicline	Placebo	RR	95% CI
Incidence of psychiatric d/o	10.7%	9.7%	1.02	0.9 - 1.2
	(excluding insomnia)			
Mood Disturbance (depressed)	2.8%	1.9%	1.4	.96 - 2.08
Anxiety Disturbance	4.5%	5.0%	.86	0.67 - 1.12
Suicidal and Self Injurious	0%	.1%	--	--
Sleep Disturbance (insomnia)	25.1%	14.5%	1.7	1.5 - 1.92

In 2016, the EAGLES trial was published,⁵⁹ and this gave further reassurance of varenicline safety. This trial, the largest and likely most rigorous of all varenicline trials, recruited approximately 8,000 participants, 50% of whom had an established/current psychiatric history (major depression, etc). A neuropsychiatric index (combination index of all neuro/behavioral/psychological adverse events) was calculated and showed clear safety of varenicline, in both psychiatric and non-psychiatric samples (figures below). The EAGLES trial served as the major impetus for FDA to remove the black box warnings. We are told that Pfizer is moving forward with OTC indication for varenicline.

Figure HS1: Summary of neuropsychiatric endpoints: EAGLES trial

Summary of primary neuropsychiatric composite safety endpoint and its components

Source: Anthenelli, et al. (2016). Neuropsychiatric safety and efficacy of varenicline, bupropion, and nicotine patch in smokers with and without psychiatric disorders (EAGLES): A double-blind, randomised, placebo-controlled clinical trial. *Lancet*

The EAGLES trial also provided a full listing of all adverse events experienced by at least 1% of the study sample. As anticipated, and per Figure above and Tables HS2 and HS3 below, those in the psychiatric cohort reported higher incidence of neuropsychiatric adverse events. The profile of adverse events exhibited (eg, abnormal dreams more common for varenicline and nicotine patch compared with placebo) was consistent with previous reports. Suicidal ideation (second table below) was reported in 0.3% of smokers in the varenicline group (non-psychiatric cohort). Overall, the treatments were well tolerated.

Table HS2: EAGLES Adverse Event Listing (reported by $\geq 1\%$ of study population)

	Non-psychiatric cohort† (n=3984)				Psychiatric cohort† (n=4074)			
	Varenicline (n=990)	Bupropion (n=989)	Nicotine patch (n=1006)	Placebo (n=999)	Varenicline (n=1026)	Bupropion (n=1017)	Nicotine patch (n=1016)	Placebo (n=1015)
Psychiatric disorders	315 (32%)	332 (34%)	301 (30%)	259 (26%)	405 (39%)	435 (43%)	420 (41%)	354 (35%)
Abnormal dreams	83 (8%)	47 (5%)	111 (11%)	39 (4%)	118 (12%)	84 (8%)	140 (14%)	53 (5%)
Agitation	32 (3%)	29 (3%)	28 (3%)	25 (3%)	47 (5%)	56 (6%)	39 (4%)	41 (4%)
Anger	3 (<1%)	1 (<1%)	1 (<1%)	3 (<1%)	11 (1%)	4 (<1%)	4 (<1%)	5 (<1%)
Anxiety‡	46 (5%)	64 (6%)	45 (4%)	57 (6%)	86 (8%)	105 (10%)	93 (9%)	63 (6%)
Depressed mood	31 (3%)	13 (1%)	27 (3%)	29 (3%)	47 (5%)	47 (5%)	52 (5%)	52 (5%)
Depression	17 (2%)	13 (1%)	8 (1%)	15 (2%)	49 (5%)	45 (4%)	47 (5%)	46 (5%)
Depressive symptom	5 (1%)	3 (<1%)	2 (<1%)	2 (<1%)	11 (1%)	8 (1%)	12 (1%)	13 (1%)
Initial insomnia	7 (1%)	6 (1%)	10 (1%)	4 (<1%)	15 (1%)	8 (1%)	10 (1%)	2 (<1%)
Insomnia	95 (10%)	126 (13%)	91 (9%)	73 (7%)	94 (9%)	119 (12%)	104 (10%)	66 (7%)
Irritability	34 (3%)	29 (3%)	47 (5%)	37 (4%)	48 (5%)	42 (4%)	61 (6%)	67 (7%)
Major depression	3 (<1%)	0	1 (<1%)	3 (<1%)	7 (1%)	10 (1%)	4 (<1%)	2 (<1%)
Middle insomnia	7 (1%)	15 (2%)	13 (1%)	6 (1%)	11 (1%)	16 (2%)	13 (1%)	8 (1%)
Nervousness	14 (1%)	18 (2%)	11 (1%)	9 (1%)	21 (2%)	19 (2%)	17 (2%)	27 (3%)
Nightmare	9 (1%)	7 (1%)	26 (3%)	3 (<1%)	13 (1%)	9 (1%)	30 (3%)	14 (1%)
Panic attack	2 (<1%)	7 (1%)	2 (<1%)	3 (<1%)	9 (1%)	19 (2%)	13 (1%)	11 (1%)
Restlessness	14 (1%)	14 (1%)	15 (1%)	14 (1%)	17 (2%)	20 (2%)	14 (1%)	9 (1%)
Sleep disorder	31 (3%)	37 (4%)	17 (2%)	19 (2%)	34 (3%)	36 (4%)	28 (3%)	23 (2%)
Tension	2 (<1%)	10 (1%)	2 (<1%)	2 (<1%)	9 (1%)	5 (<1%)	10 (1%)	6 (1%)

Table HS3: Suicidal Ideation & Behavior: EAGLES trial

	Non-psychiatric cohort* (n=3984)				Psychiatric cohort* (n=4074)			
	Varenicline (n=990)	Bupropion (n=989)	Nicotine patch (n=1006)	Placebo (n=999)	Varenicline (n=1026)	Bupropion (n=1017)	Nicotine patch (n=1016)	Placebo (n=1015)
During treatment and ≤ 30 days after last dose								
Assessed	988	983	996	995	1017	1012	1006	1006
Suicidal behaviour and/or ideation	7 (1%)	4 (<1%)	3 (<1%)	7 (1%)	27 (3%)	15 (1%)	20 (2%)	25 (2%)
Suicidal behaviour†‡	0	0	1 (<1%)	1 (<1%)§	0	1 (<1%)	0	2 (<1%)
Suicidal ideation	7 (1%)	4 (<1%)	3 (<1%)	6 (1%)	27 (3%)	15 (1%)	20 (2%)	25 (2%)
During follow-up (>30 days after last treatment dose and through end of study)								
Assessed	807	816	800	805	833	836	824	791
Suicidal behaviour and/or ideation	3 (<1%)	2 (<1%)	3 (<1%)	4 (<1%)	14 (2%)	4 (<1%)	9 (1%)	11 (1%)
Suicidal behaviour†¶	0	1 (<1%)	0	0	1 (<1%)	0	1 (<1%)	1 (<1%)
Suicidal ideation	3 (<1%)	2 (<1%)	3 (<1%)	4 (<1%)	14 (2%)	4 (<1%)	9 (1%)	11 (1%)

In the current pilot trial, we provide a 4-week mailed sample of varenicline (.5mg BID; as compared to 1mg BID as per convention) to smokers who do and do not want to quit, with minimal direct involvement from clinician. Each of these study elements has precedent (see Table HS4 below). The only design issue that is truly unprecedented here is the self-determined/self-paced use of varenicline, i.e., sampling. Though this does require added instructions for titration/use, we do not believe this does anything to increase risk. Sampling could lead to haphazard use, using some days but not others. This is an outcome we will track, but for purposes here, we view inconsistent use as similar to <100% compliance that would be anticipated for any conventional RCT of varenicline for smoking cessation. Less than full compliance is the norm for any medication trial; sampling messaging merely more accepting of it.

Table HS4: Current Pilot Trial vs. Prior RCTs of Varenicline: Comparison of Methods

	No Direct Clinical Interview	Mailed Varenicline?	Includes unmotivated smokers?	.5mg BID dosing?	≤1 month medication duration?	Self-Determined/Self-Paced Used?
Biazzo et al 2010 ⁷³	X	X			X	
Ebbert et al 2015 ⁶⁵			X			
Fouz-Rosón et al 2017 ⁹⁹				X		
Niaura et al 2008 ¹⁰¹						X
Oncken et al 2006 ¹⁰⁰				X		
Renard et al 2012 ⁶⁷						[flexible quit dates]
Rojewski et al (in press) ⁷⁴	X				X	
Selby et al 2015 ⁷⁵	X	X				
Sansores et al 2016 ¹¹⁶			X			
Swan et al 2010 (COMPASS trial) ⁷⁶	X	X				
Current pilot RCT	X	X	X	X	X	X

1.3.2 Diversion to other smokers, non-smokers: We will be mailing varenicline (a prescription medication) to participant's home address, and there is potential that someone else other than the study participant could use it.

1.3.3 Loss of confidentiality: A final risk is loss of confidentiality.

2. Adequacy of Protection Against Risks

2.1 Recruitment and Informed Consent

All research personnel have up to date CITI Certification for Protection of Human Subjects, and will keep this training current throughout the course of the study. Study participants will be recruited through statewide media outlets, including social media. Potential participants will be screened online (redcap survey) to determine study eligibility. Eligible participants will provide contact information, and either receive (their preference) 1) a mailed packet with consent form (2 copies), baseline survey, along with postage paid return envelope, or 2) doxy.me teleconsent. We have used each of these consenting options in our prior and ongoing trials. On all

correspondence with potential participants, we provide our toll-free number if any questions or problems arise. A returned, signed consent form will comprise the consented sample; in the past, about 45-50% of individuals who are mailed a consent return it; we do not badger those who decline. However, not all consenting individuals are able to be reached (~10% from previous studies) and those that are (~90%) will comprise the intent-to-treat enrolled sample. Thus, to reach our intended sample of 100 enrollees, we plan for consent of up to 120 consented. We will abide by all HIPAA regulations as set forth by our institution. The PI will supervise all aspects of the recruiting process.

2.2 Protection Against Risk

2.2.1 Use of Varenicline Participants will be screened for eligibility for varenicline. Our eligibility criteria are largely more constrictive than many of the RCTs for varenicline, most notably the EAGLES trial. We screen out for current suicidal ideation or any past attempt, as well any major psychoses (schizophrenia, bipolar). We will also exclude smokers who have a history of seizures from participating. Smokers who report pregnancy or breast-feeding will also be excluded, and females (age \leq 55yrs) will be mailed a pregnancy test to confirm. Language is included in the consent form that women should not be pregnant, breastfeeding, or planning to become pregnant.

Our dosing is .5mg BID, lower than most prior RCTs (though we do allow for smokers to decide, if they want, to titrate to 2mg). Two studies have shown roughly similar efficacy rates of 1mg (vs. 2mg), with fewer side effects and one other allowed smokers to self-titrate as they wish. Thus, we: a) provide .5mg tablets only, 56 total, b) with instructions to titrate as noted within instructions below, c) give instructions to take no more than two in the morning and two in the evening, d) give the participant the ultimate choice to self-pace usage. This choice and pattern of titration becomes an interesting study outcome that aligns with our focus on feasibility/viability. It is also wholly consistent with our naturalistic intent. Thus, we view the sampling experience as lasting 2-4 weeks depending on participant choice. For anyone who might ignore the titration schedule and either start or restart with 2mg, nausea is the most likely consequence, nothing worse.

During our phone call and within our mailings, we will include instructions to:

- Start with 1 pill per day (morning) for three days
- Then take 2 pills per day (once in morning and once in evening) for a week
- Then, if you want, you can go up to 2 pills in the morning and 2 in the evening
- Take no more than 4 pills per day
- If you ever stop taking the medication, but wish to re-start, begin again with 1 pill per day for three days

Only study team members who are involved in recruitment and data collection will have access to PHI. We will use the participant's name and phone number for prescreening documents, which will be stored in a password protected file on a secure network drive at MUSC. Subject names and numbers will be deleted from the file at the close of the study (after analyses are complete).

3. Potential Benefits of the Proposed Research to the Participants and Others / Importance of the Knowledge to be Gained

As for benefit to study enrollees, all participants will receive a referral to the SC Quitline, an evidence-based, free, and anonymous service. Half of the participants will receive a 1 month supply of varenicline, inarguably the best available cessation medication. We do expect higher rates of treatment engagement, and cessation-related behavior (quit attempts, abstinence) among those who receive varenicline.

4. Importance of Knowledge to be Gained

We have previously shown the pragmatic value of medication sampling as a method to get more smokers to make better quit attempts sooner. Whether the same rationale applies for varenicline is unclear. It would be a leap to suggest that varenicline sampling would compare to NRT sampling, and this is the very reason why this proposal offers innovation. Indeed, if varenicline sampling is found not effective to promote quitting, then this would suggest: a) sampling should be restricted to OTC products, b) sampling should be restricted to products that do not have rigid instructions for administration, and/or c) physician guidance is needed for varenicline use. In contrast, if varenicline sampling does show promise, then this would further demonstrate that minimal provider involvement is adequate, which further diminishes barriers to access. Either way, we believe this is an important research question and will answer some important questions for our field. We are unaware of any randomized controlled trial that tests varenicline sampling. Much like our prior work on NRT sampling, we believe that varenicline sampling will be a catalyst for cessation, motivating more smokers to make better, evidence-based quit attempts sooner.

5. Data and Safety Monitoring Plan

5.1 Summary of the Protocol

This application proposes a pilot RCT to determine the feasibility of varenicline sampling, as well as assess early determinants of intervention mechanism and effect sizes as compared to non-sampling control condition. Adult smokers (N=100 enrollees, up to 120 consented) from across South Carolina will be recruited via print and social media outlets. With the exception of varenicline medication, our methods strictly adhere to our prior RCTs of NRT sampling, also done remotely. Thus, a central focus here is whether varenicline sampling, as delivered remotely, is feasible to do. Participants will be screened for eligibility criteria, more conservatively than prior RCTs, including seminal EAGLES trial. Upon consent, they will be randomized to receive a one-time, 4-week sample of varenicline (.5mg tablets, 56 tablets maximum) or not. The selected dosage balances competing perspectives to: a) provide maximum therapeutic benefit, while b) not imposing undo confusion of escalating with varying dosages, and c) giving the participant ultimate choice of use. All participants are asked to complete daily diaries during the sampling period, and follow-up assessments will continue for 12 weeks beyond study enrollment. As a pilot study, our main focus is on 1) feasibility: operationally defined as: a) efficiency of recruitment (goal: 5/month, b) use of medication (incidence, quantity, patterns of use), and c) adverse events, 2) Mechanisms include measures of motivation, confidence, knowledge of and attitudes toward medication, autonomy to quit, expectancies, and cessation fatigue, and 3) early estimation of treatment effect size (cessation related-outcomes: quit attempts, medication conversion), all of which will inform a larger trial.

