A large-scale trial of varenicline sampling is premature, largely because we do not know if this is even viable. We therefore propose a pilot clinical trial with **primary aims** to: 1) determine feasibility (recruitment, compliance, retention), 2) further evaluate our hypothesized mechanisms (some from our NRT work but others new), and 3) assess preliminary effect sizes, all of which would guide a subsequent trial. We will recruit 100 smokers across our state and randomize them to receive a 4-week sample of varenicline, or not, and will follow all for 3 months. Our statewide focus derives from our hands-off (i.e., translatable) intent, such as would be eventually implemented in busy real world clinical practice (eg. primary care), yet our methods include daily diary assessment to enhance rigor. We are mindful of requirements for physician oversight, and embed full precautions for safety. Our study sample will include smokers both wanting to quit and not (purposeful recruitment of each, with stratified randomization), which will allow for exploratory sensitivity analyses to assess the role of smoker motivation on outcomes. We hypothesize that: 1) varenicline sampling will be feasible to deliver (efficient recruitment among all-comer smokers) with reasonable compliance (>80% of study sample using meds on at least 50% of sampling period), with 2) greater relative increases in all hypothesized mediators, and 3) greater increases in a range of cessation-related behavior: a) further treatment engagement (i.e., further medication use, calls to quitline), b) quit attempts, c) cessation. We are underpowered for tests of mediation and for cessation outcomes. Nonetheless, these effect sizes, as well as the larger lessons learned from this pilot RCT, will guide a larger trial. If varenicline sampling were to show promise through this and future trials, this would offer great dissemination appeal to physicians, quitlines, etc. in that, much like our NRT work, varenicline sampling could be a **pragmatic strategy to engage more smokers in better treatments, sooner**.

Human Subjects Research

1. Risks to Human Subjects

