5.2 Trial Management

All aspects of the study will be run through the MUSC Department of Psychiatry and Behavioral Sciences, where the PI holds faculty appointment. The target population is described in Section 1.1 of Human Subjects Protections, and the adjoining Planned Enrollment Table. The study timetable is as follows:

	Year 1 (months)	Year 2 (months)
Refine all procedures / IRB	1-2	
Procure supplies	2-3	
Hire and Train Personnel	3-4	
Study Enrollment		
Cumulative N to start**	(40)	(100)
First Participant Starts	5	
First Participant Completes	8	
Last Participant Starts		19
Last Participant Completes		23
Data Analysis		23-24
Manuscript Preparation		24

All numbers reflect months within total study duration (**with the exception of cumulative N)

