5.7 Trial Efficacy

Given two-year scope of pilot trial, we do not plan for interim analyses of efficacy. However, the DSMB may request an interim efficacy report to review while trial is ongoing. Final efficacy analysis will occur after all participants have completed all visits. As a behavioral intervention, our sampling approach is not blinded.

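### The recruitment goal of 5 per month (5.1) and the study timetable (5.2) are inconsistent: the goal gives 75 starts, not 100, by the planned last start in month 19, and reaches 100 only in month 24.

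*Combined protocol and SAP*

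**What the plan says.** The first primary aim in the Specific Aims is to "determine feasibility (recruitment, compliance, retention" and related elements. Hypothesis 1 predicts that "varenicline sampling will be feasible to deliver (efficient recruitment among all-comer smokers", with a numeric criterion for compliance but none for recruitment. The only number for recruitment efficiency is in 5.1, where feasibility is "operationally defined as: a) efficiency of recruitment (goal: 5/month".

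The timetable in 5.2 gives, in study months:

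- first participant starts: month 5
- "Cumulative N to start": 40 in the Year 1 column, 100 in the Year 2 column
- "Last Participant Starts": month 19
- "Last Participant Completes": month 23
- data analysis: months 23-24

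Section 5.1 adds that "follow-up assessments will continue for 12 weeks beyond study enrollment", and 5.7 begins "Given two-year scope of pilot trial". Section 1.1 defines enrolment as completing the Week 0 call, sets the intended sample at 100 and caps it there. The supplied text states no ramp-up, no second recruitment rate, and no rule for closing recruitment on a date.

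**The concern.** The goal and the timetable describe the same accrual, so one should deliver the other. They agree in Year 1 and then part. Feasibility is the first primary aim, recruitment is its first-listed element, and the result is meant to inform a larger trial. With two yardsticks that disagree, a trial that meets its stated goal exactly would also be well behind its own schedule, and the text does not say which of the two defines efficient recruitment. What is at stake is how recruitment feasibility is judged and carried forward. The treatment comparison is not at stake.

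**Working it through.** **Inputs.** Goal of 5 per month (5.1). First start in month 5, last start in month 19, last completion in month 23, cumulative starts of 40 and 100 (5.2). Follow-up of 12 weeks, about 2.8 months (5.1). Formula: cumulative starts = rate x recruiting months.

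**Reproducing the Year 1 figure.** Months 5-12 counted inclusively are 8 months, and 8 x 5 = 40, exactly the Year 1 entry. Elapsed months would give 7 x 5 = 35. The match suggests that the goal counts starts and that months are counted inclusively.

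**Starts by month 19.**

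- Inclusive: 19 - 5 + 1 = 15 months; 15 x 5 = 75, which is 25 short of 100.
- Elapsed: 19 - 5 = 14 months; 14 x 5 = 70.
- Months 13-19 alone: 7 x 5 = 35, against the 60 still needed.

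**When 5 per month reaches 100.** 100 / 5 = 20 months, so months 5-24. Equivalently, 40 + 12 x 5 = 100. The goal therefore fits both cumulative entries and conflicts with the month-19 last start and the dates after it. Follow-up would end at 24 + 2.8 = 26.8, about month 27. With the timetable's own gap between last start and last completion (23 - 19 = 4 months), it would be month 28. The plan has month 23.

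**Rate that month 19 requires.**

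- Average: 100 / 15 = 6.7 per month (100 / 14 = 7.1 by elapsed months). 6.67 / 5 = 1.33, one third above the goal.
- After 40 in Year 1: 60 / 7 = 8.6 per month in months 13-19.

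**Other readings of the goal.**

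- As consents: 75 x 100/120 = 62.5, or 75 x 0.9 = 67.5 enrolled by month 19 (using the planned 120 consents for 100 enrollees in 1.1, or the roughly 90% reached in 2.1). The gap widens.
- As a rate per arm: 8 x 10 = 80 in Year 1 and 15 x 10 = 150 by month 19. Neither figure matches.

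No reading tried gives both 40 in Year 1 and 100 by month 19.

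**Safety monitoring.** The interim board meeting in 5.9 is tied to 50% recruitment, which is a count. At 5 per month the 50th start falls in month 14 (months 5-14, 10 x 5 = 50). On the timetable it also falls in month 14 (12 + 10/8.57 = 13.2), if Year 2 accrual is assumed even.

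**The case against.** The strongest reply is that nothing shows 5 per month to be wrong. Continued to the end of Year 2, it reproduces both cumulative entries, so the misfit may lie in the dates. This stands, and the fix must not presume which side is in error. It does not remove the conflict, because recruiting to month 24 contradicts the stated last start and leaves no room for 12-week follow-up within two years.

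A second reply is that the figure is called a goal, not a pass/fail threshold, and may have been meant as a minimum or a Year 1 rate. That is possible. Section 5.1 is a summary, and the bracket holding the figure never closes, so a qualifier may have been lost. Section 5.3 also refers to an analysis plan in a Section C3f that is not in the supplied documents. The supplied text, however, gives no such label and no Year 2 rate.

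A third reply is that the consequence is small, since any report giving starts with dates would show true accrual, and the timetable is coarse (3 months from start to completion for the first participant, 4 for the last). This also stands and limits the severity. One month of coarseness does not account for a five-month difference in the last start.

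A reader might infer that the trial would end with only 75 to 99 participants if accrual averaged 5.0 to 6.6 per month. Those are the counts at month 19 (5.0 x 15 = 75; 6.6 x 15 = 99). They are final counts only if recruitment closes on that date, and no section says that it does.

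**Conclusion.** The inconsistency holds. A constant 5 per month from month 5 gives 75 of 100 starts by month 19 (70 by elapsed months). It reaches 100 five months later than planned, with follow-up ending about four months after the planned last completion and about three months after the two-year project ends. Meeting the stated goal is thus compatible with falling behind the timetable. That means a late finish if N=100 governs, or fewer than 100 participants if the dates govern, and the documents do not settle which.

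The conclusion assumes constant accrual and a goal that counts starts; the Year 1 match supports both, and counting consents would widen the gap. It applies to the supplied text only. It would be wrong to infer that the rate must be the faulty figure, or that the planned sample size is in doubt: N stays at 100, and power, type I error and safety are not affected. Severity is minor to moderate.

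**What to change.** Reconcile 5.1 with 5.2 before recruitment results are seen, keeping N at 100. The sponsor should choose one of these:

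1. **The dates and two-year scope stand.** Restate the goal in 5.1 as about 6.7 enrolled (Week 0 completers) per month, averaged over months 5-19 (7.1 by elapsed months).
2. **The dates stand and 5 per month is kept as a minimum or Year 1 rate.** Label it so, and state beside it the required 6.7 average, or about 8.6 per month in months 13-19 after 40 in Year 1.
3. **5 per month stands as the goal for the whole period.** Move the last start to month 24, the last completion to about month 27, and the analysis dates accordingly.

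The first two cost one figure or one clause in 5.1. The price of the first is a recruitment goal about one third harder to meet; the second makes that same requirement visible. The third costs a revised timetable that runs past two years. Study procedures do not change under any of them.
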